6.3.3 Urgent heart failure visits

Will be analyzed in a manner analogous to that described in 6.3.2.

6.3.4 Heart failure hospitalizations and urgent heart failure visits

Will be analyzed in a manner analogous to that described in 6.3.2.

6.3.5 Proportion of patients that progress to diabetes during the treatment period (within the subgroup of patients without diabetes at baseline only)

Will be analyzed in a manner analogous to that described in 6.3.2.

6.3.6 Change from baseline in average weekly loop diuretic dose (furosemide equivalent)

Change in daily loop diuretic dose will be summarized descriptively for the treatment and placebo group on the intention to treat dataset. This will be completed first on the entire cohort and then within subgroups of patients with or without diabetes. Additionally, among patients who were on loop diuretic at randomization, we will also compare the proportion of patients who had loop diuretic dose reduced or discontinued (using the average of 6- and 12-week doses, and also separately at 6 and 12 weeks).

Furthermore, daily loop diuretic dose will be also analyzed using generalized mixed models as the model used for NTproBNP, although appropriate distributions and link functions will be chosen for the given outcomes.

6.3.7 Change in NYHA Class at 6 and 12 weeks.

Proportion of patients with a Decreased, No change, and Increased NYHA at 6 and 12 weeks will be summarized for the treatment and placebo group on the intention to treat dataset and compared using χ^2 or Fisher's exact tests, as appropriate. This will be completed first on the entire cohort and then within subgroups of patients with or without diabetes.

Additionally, NYHA change category will be analyzed in a manner analogous to that of NT pro-BNP, although appropriate distributions and link functions will be chosen for the given outcome.

6.3.8 Echocardiography sub study endpoints: left atrial volume index and other measures of left ventricular diastolic function

Echocardiography sub study endpoints will be analyzed among patients enrolled in the Echocardiography sub study and in the modified ITTS dataset.

Continuous variables will be analyzed in a manner analogous to that of the primary endpoint. Categorical variables will be analyzed in a manner analogous to that described in 6.2.6.

7 SAFETY ANALYSES

Safety analyses will be performed on the safety analysis set (SAF). Total number of adverse events as well as number and proportion of patients developing adverse event(s) will be compared by treatment group. For patient level analyses multiple events will be counted once only per subject in each summary. The following safety variables will be included:

1. All cause death
2. Cardiovascular death
3. Non-fatal myocardial infarction (MI)
4. Stroke
5. Acute kidney injury (defined as doubling of serum creatinine based on the modified RIFLE criteria)
6. Adverse events (AEs).
 - Adverse events of special interest
 - Diabetic Ketoacidosis

- Volume Depletion Event (defined as hypotension, syncope, orthostatic hypotension or dehydration)
- Severe Hypoglycemic Event
- Lower Limb Amputations
- Drug Adverse Event
- Serious Adverse event
 - Resulted in death
 - In-patient hospitalization or prolonging of existing in-patient hospitalization
 - Persistent or significant disability
 - Life-threatening
 - Congenital anomaly/birth defect
 - Important medical event

Safety analyses will be restricted to adverse events that occurred between randomization and 12 weeks. Adverse events occurred between 12 weeks and 13 weeks will be presented separately in a supplemental analysis. As a sensitivity analysis, the above analysis will be repeated with events that occur 2 days after patients discontinue study drug being excluded.

9 SOFTWARE

All analyses will be performed using SAS 9.4 or higher.

10 APPENDICES

10.1 Scoring and Interpreting the KCCQ

There are 10 summary scores within the KCCQ, which are calculated as follows:

A. Physical Limitation

The Physical Limitation score corresponds to questions 1a through 1f. Responses to questions 1a through 1f should be coded numerically as follows:

- 1 = Extremely Limited
- 2 = Quite a bit Limited
- 3 = Moderately Limited
- 4 = Slightly Limited
- 5 = Not at all Limited
- 6 = Limited for other reasons or did not do the activity

If the responses to questions 1a through 1f are not values 1, 2, 3, 4 or 5 then the response is set to missing. Note that a response of 6 (Limited for other reasons or did not do the activity) is treated as a missing value. If at least three responses to questions 1a-1f are not missing, then the physical limitation score is computed by calculating the mean response and standardizing the result as follows:

$$\text{Physical Limitation} = 100 * (\text{Mean Response} - 1) / 4$$

B. Symptom Stability

The Symptom Stability score corresponds to question 2. Responses to question 2 should be coded numerically as follows:

- 1 = Much Worse
- 2 = Slightly Worse
- 3 = Not Changed
- 4 = Slightly Better
- 5 = Much Better
- 6 = I've had no symptoms over the last 2 weeks

If the response is 6 (no symptoms over last 2 weeks) then set the response to 3 (not changed). If question 2 is not missing then the symptom stability score is computed by standardizing the result as follows:

$$\text{Symptom Stability} = 100 * (\text{Response} - 1) / 4$$

C. Symptom Frequency

The Symptom Frequency score corresponds to questions 3, 5, 7 and 9. The responses should be coded sequentially (1, 2, 3...) in order of increasing health status as follows:

Question 3

- 1 = Every Morning
- 2 = 3 or more times per week, but not every day
- 3 = 1-2 times a week
- 4 = Less than once a week
- 5 = Never over the past 2 weeks

Questions 5 and 7

- 1 = All of the time
- 2 = Several times per day
- 3 = At least once a day
- 4 = 3 or more times per week, but not every day
- 5 = 1-2 times per week
- 6 = Less than once a week
- 7 = Never over the past 2 weeks

Question 9

- 1 = Every night
- 2 = 3 or more times a week, but not every day
- 3 = 1-2 times a week
- 4 = Less than once a week
- 5 = Never over the past 2 weeks

If two or more responses are missing then symptom frequency cannot be computed and will be missing. Otherwise, the symptom frequency is computed by calculating the mean of the standardized responses and multiplying by 100 as follows:

$$\text{Symptom Frequency} = 100 * \text{Mean}((Q3 - 1)/4, (Q5 - 1)/6, (Q7 - 1)/6, (Q9 - 1)/4)$$

D. Symptom Burden

The Symptom Burden score corresponds to questions 4, 6 and 8. The responses should be coded numerically as follows:

- 1 = Extremely Bothersome
- 2 = Quite a bit Bothersome
- 3 = Moderately Bothersome
- 4 = Slightly Bothersome

5 = Not at all Bothersome

6 = I've had no swelling (fatigue, shortness of breath)

If a response is 6 (none) then set the response to 5 (not at all). If at least one response is present then symptom burden score is computed by calculating the mean response and standardizing the result as follows:

$$\text{Symptom Burden} = 100 * (\text{Mean Response} - 1) / 4$$

E. Total Symptom Score

The total symptom score is calculated as the mean of the symptom frequency score and symptom burden score.

F. Self-Efficacy

The Self-Efficacy score corresponds to questions 10 and 11. Responses to questions 10 and 11 should be coded sequentially (1, 2, 3, 4, 5) in order of increasing health status, with 1 denoting the response associated with the lowest health status. If at least one question response is present then the self-efficacy score may be computed by standardizing the mean response as follows:

$$\text{Self-Efficacy} = 100 * (\text{Mean Response} - 1) / 4$$

G. Quality of Life

The Quality of Life score corresponds to questions 12, 13 and 14. Responses to questions 12, 13 and 14 should be coded sequentially (1, 2, 3, 4, 5) in order of increasing health status, with 1 denoting the response associated with the lowest health status. If at least one question response is present then the quality of life score may be computed by standardizing the mean response as follows:

$$\text{Quality of Life} = 100 * (\text{Mean Response} - 1) / 4$$

H. Social Limitation

The Social Limitation score corresponds to questions 15a through 15d. These responses should be coded numerically as follows:

- 1 = Severely Limited
- 2 = Limited Quite a bit
- 3 = Moderately Limited
- 4 = Slightly Limited
- 5 = Did Not Limit at All
- 6 = Does not apply or did not do for other reasons

If the responses to questions 15a through 15d are not values 1, 2, 3, 4 or 5 then the response is set to missing. Note that a response of 6 is treated as a missing value. If at least two question responses are present then the social limitation score may be computed by standardizing the mean response as follows:

$$\text{Social Limitation} = 100 * (\text{Mean Response} - 1) / 4$$

I. Clinical Summary Score

The clinical summary score is calculated as the mean of the physical limitation score and total symptom score.

J. Overall Summary Score

The overall summary score is calculated as the mean of the physical limitation score, total symptom score, quality of life score and social limitation score.

10.2 Protocol deviations

Number	Important Protocol Deviations Criteria	Major Impact on Analysis (MIA)/Other	Exclusion level
1. Did not fulfil eligibility criteria – inclusion criteria:			
1.1	Ability to provide informed consent prior to initiating screening visit procedures	MIA	Complete exclusion from PPS and MODIFIED ITTS
1.2	Age > 18 and < 120 at the screening visit	Other	No exclusion
1.3	Ejection fraction (EF) \geq 45% as determined on imaging study within 24 months of enrolment with no change in clinical status suggesting potential for deterioration in systolic function	Other	To be decided on a case by case basis
1.4	Elevated NT-proBNP (\geq 225 pg/ml) or BNP (\geq 75 pg/ml)	Other	To be decided on a case by case basis
1.5	Stable medical therapy for heart failure for 15 days	Other	To be decided on a case by case basis
1.6	On a diuretic \geq 15 days prior to screening visit and a stable diuretic therapy for 7 days	Other	To be decided on a case by case basis
1.7	At least one of the following: 
 1. Hospitalization for decompensated HF in the last 12 months 2. Acute treatment for HF with intravenous loop diuretic or hemofiltration in the last 12 months 3. Mean pulmonary capillary wedge pressure \geq 15 mmHg or LV end diastolic pressure (LVEDP) \geq 15 mmHg documented during catheterization at rest, or pulmonary capillary wedge pressure or LVEDP \geq 25 mmHg documented during catheterization with exercise. 4. Structural heart disease 		To be decided on a case by case basis

Number	Important Protocol Deviations Criteria	Major Impact on Analysis (MIA)/Other	Exclusion level
2. Did not fulfil eligibility criteria – exclusion criteria:			
2.0	Decompensated heart failure (hospitalization for heart failure within 7 days prior to screening)	Other	To be decided on a case by case basis
2.1	History of type 1 diabetes	Other	To be decided on a case by case basis
2.2	History of diabetic ketoacidosis	Other	To be decided on a case by case basis
2.3	Estimated glomerular filtration rate (eGFR) < 20 at the screening visit by modified MDRD equation GFR (mL/min/1.73 m ²) = 175 x (Scr) ^{-1.154} x (Age) ^{-0.203} x (0.742 if female) x (1.210 if African American)	Other	To be decided on a case by case basis
2.4	Admission for an acute coronary syndrome (ST-elevation MI, non-ST-elevation MI, or unstable angina), percutaneous coronary intervention, or cardiac surgery within 30 days prior to the screening visit.	Other	To be decided on a case by case basis
2.5	Admission for cardiac resynchronization therapy (CRT) within 90 days prior to the screening visit.	Other	To be decided on a case by case basis
2.6	Planned cardiovascular revascularization (percutaneous intervention or surgical) or major cardiac surgery (coronary artery bypass grafting, valve replacement, ventricular assist device, cardiac transplantation, or any other surgery requiring thoracotomy, or transcatheter aortic valve replacement) or CRT within the 90 days after the screening visit.	Other	To be decided on a case by case basis
2.7	Participation in any interventional clinical trial (with an investigational drug or device) that is not an observational registry within 15 days of the screening visit.	Other	To be decided on a case by case basis
2.8	History of hypersensitivity to dapagliflozin	Other	To be decided on a case by case basis
2.9	For women of child-bearing potential: Current or planned pregnancy or currently lactating	Other	To be decided on a case by case basis

Number	Important Protocol Deviations Criteria	Major Impact on Analysis (MIA)/Other	Exclusion level
2.10	Life expectancy <1 year at the screening visit	Other	To be decided on a case by case basis
2.11	Patients who are volume depleted based upon physical examination at the time of the screening or randomization visit	Other	To be decided on a case by case basis
2.12	Patients currently being treated with any SGLT-2 inhibitor (dapagliflozin, canagliflozin, empagliflozin, ertugliflozin) or having received treatment with any SGLT-2 inhibitor within the 12 weeks prior to the screening visit.	Other	To be decided on a case by case basis
2.13	Average supine systolic BP <100 mmHg at the screening or randomization visit	Other	To be decided on a case by case basis
2.14	Current history of bladder cancer	Other	To be decided on a case by case basis
2.15	Donation of blood or bone marrow 12 weeks prior to the screening visit and no planned donations during the study period	Other	To be decided on a case by case basis
2.16	Heart failure due to restrictive/infiltrative cardiomyopathy, active myocarditis, constrictive pericarditis, severe stenotic valve disease, and HOCM (hypertrophic obstructive cardiomyopathy).	Other	To be decided on a case by case basis
2.17	Heart failure due to severe aortic or mitral regurgitation	Other	To be decided on a case by case basis
2.18	Severe COPD thought to be a primary contributor to dyspnea	Other	To be decided on a case by case basis
2.19	Isolated right heart failure due to pulmonary disease	Other	To be decided on a case by case basis
2.20	Active and significant ischemia thought to be a primary contributor to dyspnea	Other	To be decided on a case by case basis
2.21	Documentation of previous EF < 45%, under stable conditions, within the past 36 months	Other	To be decided on a case by case basis

Number	Important Protocol Deviations Criteria	Major Impact on Analysis (MIA)/Other	Exclusion level
2.22	Complex congenital heart disease	Other	To be decided on a case by case basis
2.23	Uncontrolled hypertension, defined as systolic blood pressure ≥ 200 mmHg during the screening visit (average value of three blood pressure measurements obtained in supine position)	Other	To be decided on a case by case basis
2.24	Any other condition that in the judgment of the investigator would jeopardize the patient's participation in the study or that may interfere with the interpretation of study data or if the patient is considered unlikely to comply with study procedures, restrictions and requirements	Other	To be decided on a case by case basis
2.25	Bariatric surgery within the past 6 months or planned bariatric surgery within the study time course.	Other	To be decided on a case by case basis
2.26	CardioMems device implantation within previous 4 weeks or planned CardioMems implantation during study period	Other	To be decided on a case by case basis
2.27	For echo substudy only: patients with ventricular paced rhythm or left bundle branch block on the most recent clinically available 12-lead electrocardiogram	Other	To be decided on a case by case basis
2.30	For echo substudy only: permanent atrial fibrillation	Other	To be decided on a case by case basis

3. Patient developed discontinuation of investigational product criteria but dosing continued			
3.0	Subject experienced an Adverse Event which in the opinion of the Investigator and/or contraindicated further dosing	Other	To be reviewed on the case by case basis
3.1	Pregnancy confirmed by a positive pregnancy test or other examinations	Other	Complete exclusion from PPS
3.2	Donation of blood or bone marrow during the study period	Other	To be decided on a case by case basis
3.3	Admission for an acute coronary syndrome (ST-elevation MI, non-ST-elevation MI, or unstable angina), percutaneous coronary intervention, or cardiac surgery during the study period.	Other	To be decided on a case by case basis
4. Patient received prohibited concomitant medication but study treatment not discontinued:			
4.4.1	SGLT2 inhibitors	Other	Only the efficacy endpoints before the start of prohibited medication will be included in PPS analysis
5. Patient received incorrect investigational treatment/dose			
5.0	Patient took incorrect treatment or damaged Investigational Drug Kit	MIA	To be decided on a case by case basis
5.1	Major compliance issues <80% or >120% compliance with IP dosing in double blind treatment period	MIA	To be decided on a case by case basis
5.2	Patient randomized but never took IP	MIA	To be decided on a case by case basis

5.3	Overdose	MIA	To be decided on the case by case basis
6. Protocol-required procedure not adhered to:			
6.0	Study data collection has not been stopped when subject decided to withdraw their consent from the study completely	Other	No exclusion from PPS Data collected after consent withdrawal to be excluded from data base
6.1	Patients with absence of NT-proBNP data at randomization visit and having values at Screening visit.	Other	No exclusion from PPS Values from screening visit will be used to impute the values at randomization visit.
6.2	Patients with absence of baseline NT-proBNP data at both screening and randomization visits	Other	Excluded from the NT-proBNP analyses
6.3	Patients with no NT-proBNP values after randomization	Other	Excluded from the NT-proBNP analyses
6.4	Patients with absence of baseline KCCQ clinical summary score at randomization visit	Other	Excluded from the ITTS KCCQ analyses
6.5	Patients with no KCCQ clinical summary score after randomization	Other	Excluded from ITTS KCCQ analyses
6.6	Patients with absence of baseline 6-minute walk assessment at randomization visit	Other	Excluded from the 6-minute walk analyses
6.7	Patients with no 6-minute walk assessment after randomization	Other	Excluded from 6-minute walk analyses
6.8	Patients with missing values in the covariates: gender, Hx AFib, AFib type, Hx DM, eGFR at randomization, lvef at randomization	Other	No exclusion from PPS Excluded from the first and second primary analysis

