5.9.6 Patient refuses any form of follow-up

If the patient refuses any form of follow-up, he/she officially withdraws from the study and withdraws consent. This decision must be documented. At the end of the study, vital status on all such patients will be collected from publicly available sources, in accordance with local regulations.

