5.10 Withdrawal from study

Patients are at any time free to withdraw from the study (i.e., discontinue study medication permanently and withdraw from visit assessments), without prejudice to further treatment (withdrawal of consent). Withdrawal of consent from the study must be ascertained and documented by the investigator. Such patients will always be asked about the reason(s) and the presence of any AEs. The reason for permanent discontinuation of treatment with the study medication and the date of the last intake of the study medication must be documented.

5.10.1 Patients permanently discontinuing from study medication should be given conventional therapy, if applicable, and should always be asked to continue to attend protocol visits

If the patient denies any additional protocol follow-up and officially withdraws consent from the study one of the alternatives a) to c) should be followed:

- At the time of discontinuation of treatment and withdrawal of consent from continued assessment the patient should, if possible, undergo the PTDV. The patient should return all study medication
- If the patient does not agree to this option (which must be documented), a modified PTDV (eg, a telephone contact) should be arranged. The approach taken should be documented. The patient should return all study medication
- If the patient does not agree to a) or b) this must be documented in the patient's medical record. The patient should return all study medication.

To ensure validity of study data, it is very important to collect as much data as possible throughout the study and especially vital status (dead or alive) at the SCV. The investigator or delegate will therefore attempt to collect information on all patients' vital status from publicly available sources at the SCV, in accordance with local regulations, even if informed consent has been withdrawn completely.

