4.3 Exploratory Outcome Variables

- Composite mean hierarchical-rank clinical score.

All patients will receive a global rank endpoint based on time to death (tier 1), time to HF hospitalization or urgent HF visit (tier 2), or change in KCCQ clinical summary score from baseline to 12 weeks. The variable for ranking the patients will be derived as follows.

- Patients dying during the study will have a value of $0 + (\text{study days from randomization to death})$. Patients with missing vital status at the end of trial will be excluded from the analysis. Patient dying during the study but with no mortality date will use the average of the last known alive date and the patient's scheduled 12 weeks follow-up date.

- Patients who did not die but had multiple occurrences of HF hospitalization or urgent HF visit will have a value of 200 – number of occurrences.
- Patients who did not die but have only one HF hospitalization or urgent HF visit will have a value of 200 + (study days from randomization to the occurrence of HF hospitalization or urgent HF visit). Patients known to have an event but event date is unknown will be imputed using the median rank based on the rank of other patients in this category.
- Patients who did not die and did not experience HF hospitalization or urgent HF visit will have a value of 400 + (change in KCCQ clinical summary score from baseline to week 12).

Patients with missing KCCQ at 12 weeks who didn't die and didn't have HF events will be excluded. A sensitivity analysis will be performed where these patients will be kept in the analysis and the KCCQ values will be imputed using multiple imputation as described in section 2.6.

- Number of heart failure hospitalizations and proportion of patients experienced heart failure hospitalizations
- Number of urgent heart failure visits and proportion of patients with urgent heart failure visits
- Total number of heart failure hospitalizations and urgent heart failure visits and proportion of participants who experienced any heart failure hospitalizations and urgent heart failure visits.

For the four endpoints above, only events positively adjudicated by the clinical event committee will be included. Events that occurred between screening and randomization, and between 12 weeks and 13 weeks will be excluded from this analysis. Events that occurred between the week 12 and week 13 study visits will be reported in a separate, supplemental analysis.

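### Read literally, SAP 10.2 item 6.0 discards the vital status that the protocol seeks after consent withdrawal; the row needs an explicit exemption

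*SAP*

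**What the plan says.** **Protocol.** For a patient who refuses all follow-up and so withdraws consent, section 5.9.6 states: "At the end of the study, vital status on all such patients will be collected from publicly available sources, in accordance with local regulations". Section 5.10.1 has the site attempt to obtain "vital status from publicly available sources at the SCV, in accordance with local regulations, even if informed consent has been withdrawn completely", and gives the validity of the study data as the reason.

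**SAP 10.2, item 6.0.** The row stands under the heading "Protocol-required procedure not adhered to". Its criterion is "Study data collection has not been stopped when subject decided to withdraw their consent from the study completely". Its exclusion level leaves the patient in the per-protocol set but adds "Data collected after consent withdrawal to be excluded from data base".

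**SAP analyses that use vital status.**
- SAP 3.2 tabulates known vital status at study end, and deaths, with all randomized patients as denominator.
- SAP 7 lists all-cause death first among the safety variables. It is analysed on the safety set, and the main analysis runs from randomization to 12 weeks.
- SAP 4.3 puts death in tier 1 of the hierarchical composite and adds "Patients with missing vital status at the end of trial will be excluded from the analysis".

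**The concern.** The protocol and item 6.0 describe the same state, complete withdrawal of consent, and give different instructions for it. The protocol singles out vital status as the one item still to be pursued. The SAP row orders data from that period out of the database and does not exempt that item. A programmer who follows the row as written would remove what the sites were asked to find, and one who follows SAP 3.2 would keep it. The two would report different numbers of deaths and different vital-status completeness from the same trial.

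At stake are the first-listed safety variable, the disposition table and one exploratory endpoint. With few deaths expected, each one is visible in the safety table.

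**Working it through.** No sample size, power or event count in the plan depends on this row, so there is no plan figure to reproduce. The check is mainly a comparison of texts, followed by an illustration of size.

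**1. What changes for each kind of patient after full withdrawal**

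| Patient | Vital status kept | Item 6.0 applied literally |
|---|---|---|
| Treated, dies before week 12 | Death counted in SAP 7; tier 1 value in SAP 4.3 | In the safety set with no death counted; vital status missing, so out of the composite |
| Alive, HF event before withdrawal | Tier 2 value | Vital status missing, so out of the composite |
| Alive, no HF event, no week-12 KCCQ | Out of the composite (SAP 4.3, 6.3.1) | Out of the composite |
| Any patient whose status was traced | Counted as known in SAP 3.2 | Counted as unknown |

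The loss in the death count can go only one way: deaths are removed and none are added. In the composite, the literal rule also removes a traced survivor who would otherwise hold a value, chiefly one with an earlier HF event.

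**2. Limits on the affected set**
- Only deaths learned of after full withdrawal are touched.
- The main safety analysis stops at week 12. Deaths in weeks 12 to 13 would be lost only from the supplemental presentation.
- The SAP 7 sensitivity analysis that drops events from 2 days after stopping study drug would in general omit these deaths anyway, because withdrawal under Protocol 5.10 includes stopping study drug.
- The composite has its own week-12 cut-off and adjudication rule (SAP 4.3).

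**3. Weight of one death or one traced patient**
- SAP 2.6 expects fewer than 10 deaths, so at most 9. One lost death is at least 1/9 = 11% of the total.
- Each traced patient whose status is deleted lowers the SAP 3.2 figure for known vital status by 1/320 = 0.3 percentage points.

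**4. Illustration of how many deaths could be affected**

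The documents give neither the number of full withdrawals nor the death risk after withdrawal. The assumed ranges are:
- W = 8 to 32 withdrawers. The upper end is the whole loss allowance, 10% × 320 = 32; the lower end is a quarter of it.
- D = 3 to 9 deaths per 320 patients.
- R = 1 to 3, the death risk of withdrawers relative to average.
- Half of follow-up remaining at withdrawal.

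Risk per withdrawer: r = (D/320) × R × 0.5. Expected affected deaths: W × r. Chance of at least one: 1 − (1 − r)^W.
- Low end: r = (3/320) × 1 × 0.5 = 0.0047; 8 × r = 0.04 deaths; chance 4%.
- High end: r = (9/320) × 3 × 0.5 = 0.0422; 32 × r = 1.35 deaths; chance 75%.

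**5. Leverage on the win ratio**

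Assume 145 patients per arm and a win ratio of 1.30, with the added death losing to everyone in the other arm. There are 145 × 145 = 21,025 pairs. Wins are 21,025 × 1.30/2.30 = 11,884, and losses are 9,141.
- One dapagliflozin death included: 11,884/(9,141 + 145) = 1.28.
- One placebo death included: (11,884 + 145)/9,141 = 1.32.

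Leaving that death out returns the ratio to 1.30, a shift of about 0.02 in either direction.

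**The case against.** The best defence is that item 6.0 is a deviation row and not a general data rule. Its heading concerns procedures that were not adhered to, and its criterion is collection that should have stopped. A public-source look-up is itself a protocol procedure, so carrying it out is no deviation, and the exclusion would then reach only visits, questionnaires and laboratory results gathered improperly. Other SAP text fits that reading. SAP 3.2 plans to report known vital status over everyone randomized, and SAP 4.3 has a rule for a death without a date, which suits deaths learned of indirectly. The protocol duty is also qualified: 5.10.1 speaks of an attempt, and both sections defer to local regulations.

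Much of this stands. The narrow reading is plausible and may be what was meant, so a reader who infers that the SAP has settled on deleting these deaths goes further than the text allows. But neither document adopts the narrow reading. The instruction is framed by when data were collected, not by whether collecting them was improper. Most rows of the table leave exclusion to case-by-case review, whereas this one is fixed and acts on the database itself. SAP 3.2 supports keeping vital status, which leaves the SAP at odds with its own row.

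A reader might also infer that the primary analysis is hit, because the premature discontinuation visit includes the KCCQ and is carried forward (SAP 2.6). The documents do not support that: Protocol 5.10.1 places the visit at the time of withdrawal, not after it.

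**Conclusion.** The conflict is real and should be resolved, but its effect is small. Read literally, item 6.0 contradicts Protocol 5.9.6 and 5.10.1 and does not fit SAP 3.2. The consequences are confined to the all-cause death count, the disposition table and the exploratory composite. The primary and secondary endpoints do not use vital status.

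On the assumptions shown, between 0.04 and 1.35 deaths would be affected, and one such death moves an assumed win ratio of 1.30 by about 0.02. These are illustrations, not estimates. In particular, 8 to 32 should not be read as an expected number of withdrawals, because Protocol 5.9 separates stopping study drug and modified follow-up from withdrawal of consent, and the 10% allowance does not distinguish them.

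A reader might infer that the mortality comparison is biased in favour of one arm. Nothing in the documents shows that withdrawal is related to prognosis in this trial, or that lost deaths would fall unequally between arms. What can be said is that the death count could be too low by an unknown, probably small, number.

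**What to change.** Add one sentence to SAP 10.2 item 6.0: vital status and date of death obtained under Protocol 5.9.6 or 5.10.1, where local regulations permit, are not subject to this exclusion and remain in the database. State that they are used for disposition (SAP 3.2), all-cause death (SAP 7) and tier 1 of the composite (SAP 4.3), within the existing randomization-to-week-12 window and adjudication rules. Keep the exclusion for all other data collected after withdrawal.

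The cost is one sentence, agreed before unblinding. No new data are needed, since the protocol already has the sites seek them.
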